9.2 Statistical Analysis

9.2.1 Primary Cohort

9.2.1.1 Randomized Trial

Analysis will follow the intent-to-treat principle with all subjects analyzed in the group to which they were randomized, regardless of actual sensor wear. The primary analysis will include all subjects in the primary cohort. Preplanned subgroup analyses will be performed separately for each of the age strata: 8 to <15 years old, 15 to <25 years old, and ≥ 25 years old.

• HbA1c

The primary outcome for this cohort is the HbA1c value at 26 weeks measured in the central laboratory. If the laboratory value is unavailable then the DCA2000 value at 26 weeks will be imputed. If neither measurement is available then the value will be imputed based on available previous lab and/or DCA2000 HbA1c measurements (baseline, 4, 8, 13 and/or 19 weeks) using Rubin's method.¹⁷

Mean \pm SD values for the 26 week HbA1c value with 95% confidence intervals or percentiles appropriate to the distribution will be given for each randomization group. Randomization groups will be compared using an ANCOVA model adjusting for baseline HbA1c and factors used to stratify the randomization. Residual values will be examined for an approximate normal distribution. If values are highly skewed then a transformation or non-parametric methods will be used instead. However, previous experience suggests that HbA1c values will follow an approximate normal distribution. A 95% confidence interval will also be given for the difference of the randomization groups based on the ANCOVA model.

Improvement of at least 0.5% from baseline to 26 weeks will be analyzed as a secondary (binary) outcome. Randomization groups will be compared using logistic regression adjusting for the same factors mentioned above in the ANCOVA model.

• Glycemic Indices

The percentage of sensor values in the target range of 71-180 mg/dL at 13 and 26 weeks (separate outcome measures) will be compared between the two randomization groups (adjusted for the type of RT-CGM that was used). The percentage of sensor values in the hypoglycemic range (≤ 70 mg/dL) also will be compared.

Percentages of sensor values in the target and hypoglycemic ranges will be calculated giving equal weight to each of the 24 hours of the day for each subject. Comparisons of the two randomization groups will be performed using analogous ANCOVA models as described above for HbA1c. Residual values will be examined for an approximate normal distribution. If values are highly skewed, then a transformation or non-parametric methods will be used instead.

Randomization groups will also be compared for the total amount of sensor data available for this analysis at 13 and 26 weeks, amount of data between 10 p.m. – 6 a.m. and the percentage of subjects requiring a second week of sensor wear.

• Hypoglycemia

Clinical hypoglycemic events will be tabulated in each treatment group, which will be compared using Fisher's exact test. For purposes of analysis, a hypoglycemic event will be defined as an event requiring assistance of another person to actively administer carbohydrate, glucagon, or other resuscitative actions. These episodes may be associated with sufficient neuroglycopenia to induce seizure or coma. If plasma glucose measurements are not available during such an event, neurological recovery attributable to the

1182 restoration of plasma glucose to normal is considered sufficient evidence that the event was induced by a
1183 low plasma glucose concentration.

1184
1185 • **Questionnaires**

1186 Mean \pm SD values or percentiles appropriate to the distribution will be given by randomization group for
1187 the total score and each subscale for each questionnaire at 26 weeks. Results will be given separately for
1188 patient (for those old enough to fill out the questionnaire) and parent responses. For questionnaires
1189 administered to both randomization groups (i.e., excluding the CGM Satisfaction Scale comparisons will
1190 be made using similar ANCOVA models as described above for HbA1c. No formal adjustment will be
1191 made for multiple comparisons.

1192
1193 • **Skin Assessments**

1194 For each scheduled visit and any unscheduled visits during which an assessment was performed
1195 tabulations will be given for percentage of subjects with dry skin, scabbing and scarring and for adverse
1196 events due to skin reaction.

1197
1198 • **Adverse Events**

1199 Adverse events will be tabulated by treatment group and statistical tests performed as appropriate.
1200

1201 **9.2.1.2 Post-RCT Observation Phase**

1202 Mean \pm SD (or percentiles appropriate to the distribution) HbA1c values will be given by randomization
1203 group at baseline, 13 and 26 weeks of phase 2. The paired t-test will be used to compare the original
1204 control group at baseline vs. 26 weeks of phase 2. A similar t-test will be used to compare the group
1205 originally randomized to the sensor at 26 weeks of phase 2 vs. baseline of phase 1 and vs. baseline of
1206 phase 2 to see if any benefit was sustained through 1 year. Similar analyses will be performed for the
1207 percentage of sensor values in the target and hypoglycemia ranges and questionnaires. The number of
1208 hours of sensor data obtained in the week prior to the 13 and 26 week visits of phase 2 will be tabulated.
1209 Any adverse events will be summarized as described above.

1210
1211 **9.2.2 Secondary Cohort**

1212 Analyses in the secondary cohort (HbA1c $<$ 7.0% at baseline) will parallel those described for the primary
1213 cohort. The percentage of sensor values \leq 70 mg/dL at 26 weeks of phase 1 will be considered the
1214 primary outcome with HbA1c treated as a secondary outcome. Analysis will follow the intent-to-treat
1215 principle with all subjects analyzed in the group to which they were randomized, regardless of actual
1216 sensor wear.

1217
1218 **9.3.3 Cost-effectiveness Analysis**

1219 The cost-effectiveness analysis will be detailed in a separate document and is summarized below.
1220

1221 The analyses will address the following objectives:

- 1222 • To collect utilities for T1D-related health states for patients and their caregivers and to measure
1223 health care utilization and economic consequences attributable to RT-CGM.
 - 1224 • To evaluate the within-trial cost-effectiveness of RT-CGM compared with standard care.
 - 1225 • To evaluate the lifetime cost-effectiveness of RT-CGM utilizing a simulation model of the
1226 complications of diabetes.
 - 1227 • To compare the lifetime cost-effectiveness of RT-CGM with perfect self-selection with lifetime
1228 cost-effectiveness based on traditional cost-effectiveness analysis.
- 1229

1230 For all analyses, the effectiveness parameter will be expressed in terms of quality-adjusted life-years
1231 (QALYS). Cost accounting will vary according to the time-frame and perspective of the analysis. The
1232 within-trial health system perspective will include all the direct costs associated with the program and all

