1.2.1 Studies on the Three RT-CGMs

FreeStyle Navigator

189 Bode et al.¹¹ reported on adults with type 1 (N=60) or type 2 (N=41) diabetes who wore a blinded
 190 Navigator sensor for an average of 287h. Patients spent an average 8% of time in the hypoglycemic
 191 range (<70 mg/dL), 63% time in euglycemia (70-180 mg/dL) and 29% time in the hyperglycemic
 192 range (>180 mg/dL). The sensor detected an average of 1.6 hypoglycemic episodes per day each
 193 lasting an average of 0.9h. No accuracy data were reported.

194

195

196

DexCom STS

197 Garg et al.¹² studied 15 adults with T1D. The mean relative absolute difference (RAD) was 16%
 198 during a 12h inpatient session compared to a home glucose meter reference and 25% compared to a
 199 YSI reference. The bias difference compared to a home glucose meter was <15% in each glucose
 200 range studied. Patients wore a blinded sensor at home for a mean of 50 days followed by a period of
 201 unblinded home use (mean 44 days). Patients spent a median 47% less time below 3.1 mmol/L and
 202 25% less time above 13.3 mmol/L (both $P < 0.05$) when the sensor was unblinded. No adverse events
 203 were reported as a result of sensor use.

204

205

The DexCom users guide reports a median RAD of 20% pooling inpatient and outpatient data.¹³

206

207

Guardian

208 Bode et al.¹⁴ randomized 71 adults with T1D to wear the Guardian sensor with either the hypo-
209 /hyperglycemia alarms turned on or off. The median RAD value was 17% with a median bias of -8
210 mg/dL compared to a home glucose meter. Both randomization groups wore two sensors (median
211 sensor life 72h) with the alarms turned off during the first period. During the second period each
212 subject wore two more sensors with the alarms activated (set to 70 and 250 mg/dL) in those
213 randomized to the alarm group. The median duration of hypoglycemic excursions dropped
214 significantly more between the two periods in the alert group (27.8 vs. 4.5 minutes; P = 0.03), but the
215 median number of hypoglycemic events increased slightly more in the alert group (+0.5 vs. +0.03 per
216 day; P = 0.18). No significant differences in the incidence or duration of hyperglycemia. Eleven
217 adverse events were reported from 7 subjects including 7 instances of mild skin irritation, 2 instances
218 of excessive bleeding (moderate intensity), 1 instance of hematoma and 1 instance of moderate
219 discomfort.

220

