619 Enrolled subjects will return 10 (+3) days after enrollment for baseline testing and randomization. The
620 purpose of the visit will include the following:

- 621 • Assessment of compliance with the use of the RT-CGM and HGM
- 622 • Assessment of skin reaction in areas where a RT-CGM sensor was worn
- 623 • Randomization to the RT-CGM Group or the Control Group
- 624 • For subjects in the RT-CGM Group, initiation of unblinded RT-CGM use
- 625 • Instruction on downloading of glucose data for those with a home computer
- 626 • Collection of blood sample to send to the central laboratory for HbA1c determination

627
628 **3.2 Review of RT-CGM and HGM Data**

629 The HGM and RT-CGM data will be downloaded and reviewed by personnel not involved with treatment
630 of the subject to assess whether the subject has been compliant.

- 631 • To be continued in the study, it will be necessary that the subject has completed at least 3 HGM
632 measurements a day since enrollment, has used the RT-CGM on at least 6 out of 7 days prior to
633 the visit, and obtained at least 96 hours of RT-CGM glucose values with at least 24 hours of
634 glucose values during the hours of 10 p.m. and 6 a.m.

635
636 Subjects not meeting these criteria may be given a second opportunity at investigator discretion to
637 complete the RT-CGM and HGM requirements.

638
639 Subjects who are unable to meet the RT-CGM and HGM compliance requirements will be withdrawn
640 from the study and not randomized.

641
642 **3.3 Randomization**

643 Subjects who have been compliant with home glucose monitoring and use of the RT-CGM will be
644 randomized to one of two treatment groups:

- 645 1. RT-CGM Group
- 646 2. Control Group

647
648 The subject's randomization group assignment is determined by entering the Randomization Visit data on
649 the study website.

- 650 • The Jaeb Center will construct a Master Randomization List using a permuted block design.
- 651 • For subjects with baseline HbA1c $\geq 7.0\%$, the randomization will be stratified by clinical center,
652 age (8-<15, 15-<25, ≥ 25) and HbA1c (7.0-8.0, 8.1-10.0).
- 653 • For subjects with baseline HbA1c $< 7.0\%$, the randomization will be stratified by clinical center
654 only.

655
656 *Once a subject is randomized that subject will be included in the data analysis regardless of whether or*
657 *not the protocol for the assigned randomization group is followed. Thus, the investigator must not*

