935 post-RCT observational phase. The number of questions may be reduced prior to initiation of its use in
936 the study. A version of this questionnaire will also be completed by the spouses of adult subjects in the
937 RT-CGM group following the 26-week visit of the RCT and by spouses of adult subjects in both groups
938 following the 26-week visit of the post-RCT observational phase. For spouses, the questionnaire will be
939 completed on paper at home and mailed back to the clinical center. Administration time is approximately
940 10-20 minutes.

941
942 **6.9 Algorithm Satisfaction Questionnaire**

943 This questionnaire was developed to measure the frequency and convenience of use of study-developed
944 algorithms and satisfaction with use of the algorithms developed for the protocol. A separate
945 questionnaire will be completed by the RT-CGM Group and the Control Group at 4 weeks and 13 weeks.
946 The Control Group will complete the RT-CGM Algorithm Satisfaction Questionnaire at 4 weeks in the
947 post-RCT observational phase. Data from this study will be used to evaluate the measure's psychometric
948 properties including internal consistency, parent-adolescent agreement, associations with study outcomes
949 and descriptive statistics. Administration time is approximately 5 minutes.

950
951

952 **CHAPTER 7**
953 **ADVERSE EVENTS**

954
955 **7.1 Definition**

956 A reportable adverse event is any untoward medical occurrence that meets criteria for a serious adverse
957 event or any unexpected medical occurrence in a study subject that is study or device-related.

958 **7.2 Recording of Adverse Events**

959 Throughout the course of the study, all efforts will be made to remain alert to possible adverse events or
960 untoward findings. The first concern will be the safety of the subject, and appropriate medical
961 intervention will be made.

962
963 The investigator will elicit reports of adverse events from the subject at each visit and complete all
964 adverse event forms online. Each adverse event form is reviewed by the Coordinating Center to verify the
965 coding and the reporting that is required.

966
967 The study investigator will assess the relationship of any adverse event to be related or unrelated by
968 determining if there is a reasonable possibility that the adverse event may have been caused by the study
969 device or study procedures.

970

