971 The intensity of adverse events will be rated on a three-point scale: (1) mild, (2) moderate, or (3) severe. It
972 is emphasized that the term severe is a measure of intensity: thus a severe adverse event is not necessarily
973 serious. For example, itching for several days may be rated as severe, but may not be clinically serious.

974
975 Adverse events will be coded using the MedDRA dictionary.

976
977 Definitions of relationship and intensity are listed on the website data entry form.

978
979 Adverse events that continue after the subject's discontinuation or completion of the study will be
980 followed until their medical outcome is determined or until no further change in the condition is expected.

981
982 **7.3 Reporting Serious or Unexpected Adverse Events**

983 A serious adverse event is any untoward occurrence that:

- 984
- 985 • Results in death
 - 986 • Is life-threatening; (a non life-threatening event which, had it been more severe, might have become
987 life-threatening, is not necessarily considered a serious adverse event)
 - 988 • Requires inpatient hospitalization or prolongation of existing hospitalization
 - 989 • Results in significant disability/incapacity
 - 990 • Is a congenital anomaly/birth defect

991 An *Unanticipated Adverse Device Event* is defined as an adverse event caused by, or associated with, a
992 device, if that effect or problem was not previously identified in nature, severity, or degree of incidence.

993
994 Serious or unexpected adverse events must be reported to the Coordinating Center immediately via
995 completion of the online serious adverse event form.
996

997 The Coordinating Center will notify all participating investigators of any adverse event that is both
998 serious and unexpected. Notification will be made within 10 days after the Coordinating Center becomes
999 aware of the event.

1000
1001 Each principal investigator is responsible for informing his/her IRB of serious study-related adverse
1002 events and abiding by any other reporting requirements specific to their IRB.
1003

1004 **7.4 Risks And Discomforts**

1005 **7.4.1 Skin Reactions**

1006 There is a low risk for developing a local skin infection at the site of the sensor needle placement.
1007 Itchiness, redness, bleeding, and bruising at the insertion site may occur as well as local tape allergies.
1008

1009 During each follow-up visit, each site where a RT-CGM sensor has been worn will be assessed by study

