1010 personnel. Both acute and non-acute changes will be assessed (as described on the case report form and
1011 in the Procedures Manual). If a skin reaction is classified as severe (the observation is extremely
1012 noticeable and bothersome to subject and may indicate infection or risk of infection or potentially life-
1013 threatening allergic reaction) an Adverse Event Form will be completed.
1014

1015 **7.4.2 Fingertick Blood Glucose Measurements**

1016 Fingerticks may produce pain and/or ecchymosis at the site.
1017

1018 **7.4.3 Psychosocial Questionnaires**

1019 As part of the study, subjects and parents will complete psychosocial questionnaires which include
1020 questions about their private attitudes, feelings and behavior related to diabetes. It is possible that some
1021 people may find these questionnaires to be mildly upsetting. Similar questionnaires have been used in
1022 previous research and these types of reactions have been uncommon.
1023

1024 The study may include other risks that are unknown at this time.
1025

1026 **7.5 Data and Safety Monitoring Board**

1027 An independent Data and Safety Monitoring Board will be informed of all serious adverse events and any
1028 unanticipated adverse device events that occur during the study and will review compiled adverse event
1029 data at periodic intervals.
1030

1031 **CHAPTER 8**
1032 **MISCELLANEOUS CONSIDERATIONS**

1033
1034 **8.1 Benefits**

1035 It is expected that RT-CGM devices will have an important role in the management of diabetes.
1036 Therefore, the results of this study are likely to be beneficial for patients with diabetes.
1037

1038 It is possible that subjects will not directly benefit from being a part of this study. However, it is also
1039 possible that the blood sugar information from the monitor along with the algorithms provided for
1040 management decisions will be useful for subjects' diabetes self-management.
1041

1042 **8.2 Subject/Parent Reimbursement**

1043 The study will provide the RT-CGM and related supplies, and the study HGM and test strips.
1044

1045 The study will be paying the subject \$25 per completed protocol-required visit to cover travel and other
1046 visit-related expenses. Additional travel expenses will be paid in select cases for subjects with higher
1047 expenses. There will be no compensation for completing telephone calls.
1048

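### Expected mild or moderate acute skin reactions to the sensor are assessed under 7.4.1 but fall in no table stated in 9.2.1.1

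*Protocol*

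**What the plan says.** **Risks and assessment (Protocol 7.4.1).** The section gives a low risk of local infection at the insertion site and then adds: "Itchiness, redness, bleeding, and bruising at the insertion site may occur as well as local tape allergies". Staff examine every site where a sensor has been worn at each follow-up visit, and "Both acute and non-acute changes will be assessed", with details left to the case report form and the Procedures Manual. An Adverse Event Form is called for when a reaction is classified as severe. That class is described as very noticeable and bothersome, with possible infection, risk of infection or a life-threatening allergy.

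**Reportable events (Protocol 7.1).** A reportable adverse event is either a serious "event or any unexpected medical occurrence in a study subject that is study or device-related".

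**Analysis (Protocol 9.2.1.1, Skin Assessments).** For each scheduled visit, and any unscheduled visit with an assessment, "tabulations will be given for percentage of subjects with dry skin, scabbing and scarring". The same sentence also covers adverse "events due to skin reaction". A separate item tabulates adverse events by treatment group.

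**Other phases and cohorts.** Section 9.2.1.2 carries the adverse event summary into the observation phase but does not mention skin assessments, although 5.3 has them done in both groups. Section 9.2.2 has the secondary cohort analyses parallel those of the primary cohort.

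**The concern.** The findings tabulated by name are not the ones that the protocol presents as the risks of wearing a sensor. An acute reaction that is expected and short of severe seems to meet neither the skin list nor the adverse event criteria. If so, the follow-up examinations would collect information on the most ordinary harm of the device, and the planned summary would leave it out. Sensor wear would look better tolerated than the assessments show. That matters for a device meant for daily use from age 8, in a trial that also weighs quality of life and cost-effectiveness.

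**Working it through.** No design figure is involved, so the check sets the sections side by side.

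**Step 1: compare the lists.**

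| Named as a risk in 7.4.1 | Tabulated by name in 9.2.1.1 |
|---|---|
| infection | no |
| itchiness | no |
| redness | no |
| bleeding | no |
| bruising | no |
| tape allergy | no |

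The three findings that 9.2.1.1 does name are dry skin, scabbing and scarring. The overlap with the six risks is 0 of 3.

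**Step 2: follow the fourth item, adverse events due to skin reaction.** A reaction enters this table only if it is recorded as an adverse event. The protocol states these routes:

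- Severe under 7.4.1: a form is completed, so the reaction is tabulated.
- Serious under 7.1: reportable, so tabulated.
- Unexpected and related to the study or device under 7.1: reportable, so tabulated.
- Listed in 7.4.1 (hence expected), mild or moderate, and not serious: none of these routes applies.

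**Step 3: combine.** The last class is within the acute changes that 7.4.1 has assessed, but it is neither a named skin finding nor an adverse event that the protocol requires to be recorded. It has no stated table.

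**Step 4: is that class common?** The only graded breakdown of non-severe events in the protocol is the Guardian study in 1.2.1, where eleven "adverse events were reported from 7 subjects including 7 instances of mild skin irritation, 2 instances" of moderate excessive bleeding, one hematoma and one moderate discomfort.

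- Events: 7 + 2 + 1 + 1 = 11.
- Mild irritation or moderate bleeding: 7 + 2 = 9, so 9 of 11.
- The hematoma has no grade. Discomfort is not a risk listed in 7.4.1 and might count as unexpected. Both are left out of the 9.

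This count assumes that irritation corresponds to the itchiness and redness of 7.4.1, and that the study's grades carry over to this trial's scale. It shows what kind of event is affected. It is not a forecast of how many there will be.

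**The case against.** **Chapter 9 is a synopsis.** It says that a detailed analysis plan will supersede it, and the choice of table rows is commonly left to that plan. Silence here would therefore be no finding. But 9.2.1.1 is not silent: it fixes a list that does not match the protocol's own risk section. The threshold for an Adverse Event Form also sits in Chapter 7, which the statement about superseding does not cover.

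**Milder events may still be recorded.** Section 7.2 has investigators elicit adverse events at each visit and grade them as mild, moderate or severe. Section 7.3 would catch a named reaction that occurs with unforeseen severity or frequency. Section 7.4.1 does not forbid a form for a milder reaction. This stands in part: some such reactions may be recorded. Nothing requires it, and 7.1 is the narrower rule, so coverage would depend on the site.

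**Stronger readings that the documents do not support.**

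- A reader might infer that only the three named findings are tabulated, or that acute reactions are reported nowhere. Skin adverse events are tabulated too, and the changes are assessed on the case report form. The gap is in the stated tables.
- A reader might infer that infections would go unseen. The definition of severe itself mentions infection, so a notable infection would probably reach a form.
- A reader might scale the Guardian rate to a minimum number of unreported subjects here. The protocol does not link events to subjects. The 9 events could lie in as few as 7 − 2 = 5 of 71 subjects, and the exposure differs. No such minimum follows.
- A reader might infer that subjects who fail the run-in appear in no table, since 3.2 says: "Subjects who are unable to meet the RT-CGM and HGM compliance requirements will be withdrawn". But the schedule in 1.6.1 and section 3.1 place a skin assessment at the randomization visit, and 9.2.1.1 tabulates each scheduled visit without limiting that sentence to randomized subjects. The text is unclear on this point, and an exclusion is not shown.

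**Conclusion.** The point holds in a limited form. Expected, non-serious skin reactions of mild or moderate intensity are assessed under 7.4.1 but belong to no table stated in 9.2.1.1, so a summary built from that list and the Chapter 7 thresholds would understate acute site reactions. Severe, serious or unexpected reactions are covered.

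The size is modest: the completeness of one safety summary is at stake, and no efficacy endpoint, test or sample size changes. How many subjects are concerned cannot be derived from the protocol. The conclusion assumes that the reactions listed in 7.4.1 count as expected, that sites apply the thresholds as written, and that the later analysis plan keeps the list. It also takes the case report form to record acute changes, as 7.4.1 says; the form itself was not available.

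**What to change.** In 9.2.1.1, replace the list of three findings with a tabulation, by treatment group and visit, of every acute and non-acute change recorded on the skin case report form. Give the worst intensity per subject, and show this alongside skin adverse events. Apply it by reference in 9.2.1.2, which now names no skin table, and in 9.2.2.

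State that the visit 0 tabulation includes enrolled subjects who were assessed but not randomized, in a column of their own.

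Note with the table that 4.2.1.1 limits skin assessment at follow-up visits of the randomized phase to the RT-CGM Group. The Control Group columns will then be filled mainly at visit 0 and in the observation phase.

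The cost is a few sentences and a few more table rows, drawn from an assessment that 7.4.1 already requires. No new visits or analyses of the primary outcome are needed.
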